4.1. Overall Design

Dronedaronone was approved in 2009 by the Food and Drug Administration to reduce the risk of CV hospitalization in patients with AF or atrial flutter. However, it is unknown if dronedaronone (or any antiarrhythmic medication) can reduce CV hospitalization or death in patients with first-detected AF. This trial has been designed to address this important question. In order to facilitate the trial enrollment, data collection, and generalizability to clinical practice, the CHANGE AFIB study has been designed as an open-label pragmatic clinical trial nested within the Get With The Guidelines (GWTG) Atrial Fibrillation registry. At present the overall GWTG program is being implemented in over 2,300 hospitals across the U.S. and is comprised of over 9 million patient records, with an estimated 650,000 new patient records entered per year. The trial will utilize the existing GWTG registry network, data collection architecture, and experience to facilitate both enrollment and conduct of the trial.

The comparator arm will be “usual care.” Thus, this study will compare usual care plus dronedaronone versus usual care alone. While usual care often varies from center to center, usual care typically consists of an atrioventricular blocking agent (beta-blocker, non-dihydropyridine calcium channel blocker, or digoxin) without an antiarrhythmic drug.[‡] As dronedaronone has anti-adrenergic rate controlling properties, a low dose of beta-blocker or calcium-channel blocker is recommended in the USPI when starting dronedaronone. In the dronedaronone arm concomitant digoxin use will be contraindicated due to P-gp interaction based upon data from the PALLAS trial.^{29,51} All patients will receive oral anticoagulation for stroke prevention according to current guideline recommendations.³³

CHANGE AFIB will leverage several critical advantages as a pragmatic clinical trial.⁵² Data collection will be integrated into the Get With The Guidelines AFIB registry.^{53,54} The use of the GWTG-AFIB registry will also enhance subject recruitment and ensure the enrollment of a diverse group of patients. The randomized intervention will be compared with usual care thus further enhancing generalizability. Follow-up visits will be minimized to reduce patient burden. Moreover, follow-up visits will have “windows” to accommodate variation in follow-up intervals at different centers.

[‡] Orally administered antiarrhythmic drugs for the treatment of atrial fibrillation include Vaughan-Williams class I and III medications, including flecainide, propafenone, sotalol, dofetilide, dronedaronone, and amiodaronone. Note, beta-blockers (class II) and non-dihydropyridine calcium channel blockers (class IV) are not membrane active antiarrhythmic medications.

4.2. Justification for Study Drug Intervention and Dose

Dronedaronone is a non-iodinated benzofuran similar to amiodarone but is not associated with thyroid or pulmonary toxicity in randomized clinical trials or post-marketing observational studies.^{55, 56} Dronedaronone has electrophysiological characteristics spanning all 4 Vaughan-Williams anti-arrhythmic classes, with primarily class III effects. Initial trials suggested that dronedaronone prolonged the time to recurrence of AF and reduced cardiovascular death and hospitalization.^{26, 27}

The landmark ATHENA trial evaluated the efficacy and safety of dronedaronone in patients with atrial arrhythmias (atrial fibrillation or atrial flutter). This trial did not include patients with a recent history of NYHA class IV heart failure or recent hospitalization for decompensated heart failure (<4 weeks). Approximately 30% of the ATHENA population had NYHA class I-III heart failure. ATHENA demonstrated that dronedaronone 400 mg twice daily (in combination with background therapy) reduced the combined endpoint of CV hospitalization or death from any cause by 24% ($p < 0.001$) compared with placebo. Of course, the ATHENA trial was not conducted in the special population of patients with a new diagnosis of AF. There are no randomized trials or guideline recommendations for antiarrhythmic therapy at the time of first-detected AF. A subgroup analysis from the ATHENA trial suggests that optimal outcomes may be achieved in those patients with shorter duration of AF (time from diagnosis).⁵⁷ Similar observations have also been made in patients undergoing other forms of rhythm control, including catheter ablation.⁵⁸ In this trial, patients with first-detected AF will be randomized to dronedaronone on top of usual care versus usual care alone. Patients randomized to the intervention arm will be prescribed and treated with Dronedaronone 400 mg bid. This dose has been chosen as it is the Food and Drug Administration approved dose as well as the dose recommended in current international guidelines.^{26, 33} Dronedaronone has also been shown to be an effective rate control agent as well. In the ERATO study, treatment with dronedaronone 400 mg twice daily led to a mean reduction of 24.5 beat/min in patients with permanent AF when compared with placebo. In the EURIDIS/ADONIS studies the mean difference in patients with paroxysmal/persistent AF during AF recurrence was 14 beats/min.²⁷ Moreover, the dronedaronone treated patients experienced improved rate control without any reduction in exercise tolerance as measured by maximal exercise.⁵⁹

5. Study Population

- Eligible patients enrolled in GWTG-AFIB who provide informed consent will undergo randomization in a 1:1 fashion, to dronedarone on top of usual care or usual care alone.

5.1. Inclusion Criteria

Participants are eligible to be included in the study if the following apply:

1. Age 21 years or older.
2. First-detected atrial fibrillation (defined as atrial fibrillation diagnosed in the previous 120 days)
3. Electrocardiographic documentation of atrial fibrillation. §
4. Estimated life expectancy of at least 1 year
5. Patient or legal authorized representative capable of giving signed informed consent, which includes compliance with the requirements and restrictions listed in the informed consent form (ICF) and in this protocol.

5.2. Exclusion Criteria

Participants are excluded from the study if any of the following criteria apply:

1. Patients with prior or planned treatment with rhythm control, either catheter ablation or chronic (>7 days) antiarrhythmic drug therapy.**
2. Planned cardiothoracic surgery
3. New York Heart Association class III or IV heart failure or a hospitalization for heart failure in the last 4 weeks
4. Patients with reduced ejection fraction (LVEF \leq 40%)
5. Permanent atrial fibrillation
6. Ineligible for oral anticoagulation, unless CHA₂DS₂-VASc is less than 3 in women or 2 in men.
7. Bradycardia with a resting heart rate < 50 bpm
8. PR interval >280 msec or 2nd degree or 3rd degree atrioventricular block without a permanent pacemaker/cardiac implanted electronic device.
9. Corrected QT interval \geq 500 msec.
10. Pregnancy or breast feeding
11. Severe hepatic impairment in the opinion of the investigator

§ Electrocardiographic documentation includes a standard 12 lead electrocardiogram, mobile ECGs, ambulatory monitoring (e.g., Holter), telemetry, or electrograms from cardiac implanted electronic devices (i.e., pacemaker).

** Acute use of an antiarrhythmic drug in the hospital is not exclusionary. For the purpose of this trial, prior antiarrhythmic drug therapy is defined as chronic antiarrhythmic drug therapy (>7 days).

6. Study Intervention, Usual Care, and Concomitant Therapy

The study intervention will be treatment with oral dronedarone 400 mg twice daily in addition to usual care. The comparator arm will be usual care alone. Usual care will be defined as best-practice, guideline-directed therapy of AF, including but not limited to (a) stroke prevention therapy, (b) rate-control, and (c) treatment of risk factors. More specifically, oral anticoagulation in those men with a CHA₂DS₋₂VASc score of 2 or greater or women with a CHA₂DS₋₂VASc score of 3 or greater, rate control, and treatment of concomitant cardiovascular conditions (e.g. coronary artery disease or heart failure) will be required in all trial participants. As defined in the protocol, those randomized to the dronedarone arm will be prescribed 400 mg oral dronedarone twice daily. Similar to the approach in the EAST trial, those randomized to usual care alone will initially be treated without rhythm-control therapy¹⁴, however rhythm-control therapy (except dronedarone) may be initiated during follow-up in the usual care arm to ameliorate AF-related symptoms despite adequate rate-control therapy per current guideline recommendations. In the dronedarone arm concomitant digoxin use is contraindicated due to P-gp interaction based upon data from the PALLAS trial.²⁹

6.1. Measures to Minimize Bias: Randomization

This is an open-label study; however, the specific intervention to be taken by an enrolled participant will be randomly assigned. Participants will be randomly assigned 1:1 to dronedarone on top of usual care or usual care alone. Randomization will be stratified by site and will be created with a random block size. All participants will be centrally assigned to randomized study intervention using an interactive web response system (IWRS). The site will contact the IWRS prior to the start of study intervention administration for each participant. The site will record the intervention assignment on the applicable case report form, if required. Potential bias will be reduced by the use of central randomization. Site staff and participants will not know the randomized sequence of treatment assignment prior to enrollment. Before the study is initiated, the log-in information and directions for the IWRS will be provided to each site.

6.2. Study Intervention Compliance

The intervention will be prescribed by the treating physician. Study drug will be supplied as part of the study. Participants in the intervention arm will have the study drug prescription generated on their behalf by the PI or treating physician. The study team will communicate with the Central Pharmacy vendor to initiate the study drug kit request and shipment direct to the subject's mailing address of choice. Subjects in the intervention arm will be contacted within 10 days of randomization to verify that they have received their study drug shipment and have started taking their prescription for dronedarone. Participants will self-administer the study intervention at home. Subjects in the intervention arm will receive 3 study drug kit shipments throughout their participation in the trial. Each study drug kit shipment will contain 4-months of study drug supply. Study drug compliance will be assessed at each visit. There is one guideline-recommended therapeutic dose of dronedarone. Any deviation(s) from the prescribed dosage regimen should be recorded. At the end of the study, the patient's physicians will determine whether to stop or continue dronedarone.

6.3. Concomitant Treatment

Concomitant drug therapy will be recorded in the case report form at baseline and all follow-up periods. In the dronedarone arm concomitant digoxin use is contraindicated due to P-gp interaction based upon data from the PALLAS trial.²⁹ Observational data have observed a small increased risk of bleeding in patients treated with dronedarone and direct acting oral anticoagulants, however, there is no apparent increased risk of intracranial bleeding.⁶⁰

Cardioversion (pharmacologic or electrical) is not an exclusion and is permitted throughout the trial. Patients who are planned or scheduled to undergo catheter ablation during screening or at the baseline visit are not eligible. Following enrollment, if a patient experiences escalation of symptoms or refractory symptoms, escalation of rhythm control interventions, including catheter ablation, can be considered if deemed necessary by the patient's treating physician.

7. Discontinuation of Study Intervention and Participant Discontinuation/Withdrawal

The end of the study is defined as the date of the last visit of the last participant in the study or last scheduled procedure shown in the schedule of activities for the last participant in the study. A participant is considered to have completed the study if he/she has completed all periods of the study including the last study visit at 12 months, or if deceased during the follow-up period.

Patients should not be discontinued when they experience a primary endpoint event. They should continue in the trial until the end of study visit at the end of follow-up. The study intervention therapy should be continued unless deemed otherwise by the treating physician or if the patient requires initiation of a different antiarrhythmic medication.

7.1. Discontinuation of Study Intervention

In rare instances, it may be necessary for a participant to permanently discontinue study intervention. If study intervention is permanently discontinued, the participant will remain in the study until they complete 12-month follow-up/final visit.

7.2. Participant Discontinuation/Withdrawal from the Study

A participant may withdraw from the study at any time at his/her own request or may be withdrawn at any time at the discretion of the investigator for safety, behavioral, or compliance reasons. This is expected to be uncommon. The participant will be permanently discontinued from the study intervention and the study at that time. If the participant withdraws consent for disclosure of future information, any data collection before withdrawal of consent can be used.

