9.2. Analysis Sets

Population	Description
Intent-to-treat (ITT)	
 • All randomized participants will be included in the analyses according to the intervention arm they were assigned,

Population	Description
	regardless of treatment initiation, discontinuation or switching.
On treatment population and on-treatment period	
 All randomized participants who took the assigned treatment will be included in the analyses according to the intervention arm they were assigned until they switch or discontinue the assigned treatment regimen. Follow-up will be censored 5 days after treatment switching or discontinuation, i.e. all events occurring until 5 days after discontinuation or switching to the other treatment group will be attributed to the randomized group and all events occurring later than 5 days after discontinuation or switching will be censored. Participants in the usual care arm who start dronedarone drug therapy will be considered to have switched treatment regimen. Participants in the dronedarone arm who temporarily suspend or are non-adherent with dronedarone for >14 consecutive days will be considered to have discontinued treatment.

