9.3.2. Primary Efficacy Estimand Analysis

Question of Interest	Does the treatment with dronedarone on top of usual care reduce cardiovascular hospitalization or death from any cause in patients with first-detected atrial fibrillation without heart failure compared to usual care alone?
Objective Description / Study Population	Primary objective of the study / All randomized participants
Endpoint	Time from randomization to the first occurrence of unplanned cardiovascular hospitalization or death from any cause within 12 months of randomization

Intercurrent Events	Early study withdrawal or lost-to-follow-up: follow-up will be censored at the last date when patient event status was known. Analysis will assume that censoring is non-informative. All other intercurrent events will be ignored in these analyses.
Population Summary	Hazard ratio estimate based on a Cox proportional hazards model. Values below 1.0 suggest benefit from the treatment with dronedarone and usual care versus usual care alone.

The Cox proportional hazards model will be fit for time to first event with the treatment group as exposure variable. The treatment effect will be presented as a hazard ratio (dronedarone on top of usual care vs. usual care) and a 95% CI and P-value.

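### Section 7.2 lets unblinded investigators end follow-up for reasons that overlap with stopping drug under 7.1, which may cause differential, informative loss of hospitalizations in the primary analysis

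*Protocol*

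**What the plan says.** Section 7.1 deals with stopping study drug: "If study intervention is permanently discontinued, the participant will remain in the study until they complete 12-month follow-up/final visit".

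Section 7.2 deals with leaving the study. Apart from the participant's own request, a participant "may be withdrawn at any time at the discretion of the investigator for safety, behavioral, or compliance reasons". The consequence is stated without exception: "The participant will be permanently discontinued from the study intervention and the study at that time". On frequency the protocol says only "This is expected to be uncommon".

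Section 9.2 defines the intent-to-treat set as all randomized participants in their assigned arm, "regardless of treatment initiation, discontinuation or switching". For early withdrawal and loss to follow-up, the primary analysis in Section 9.3.2 states: "follow-up will be censored at the last date when patient event status was known. Analysis will assume that censoring is non-informative".

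Section 6.1 confirms that the trial is open-label. Section 7.3 has sites try to obtain vital status for everyone randomized. Section 8 has the final form completed for patients who withdraw early.

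**The concern.** The same event can fall under either section. A patient in the dronedarone arm who stops taking tablets, or who has a suspected drug reaction, could be kept to 12 months at one site under 7.1 and removed at another under 7.2. Section 9.2 itself counts more than 14 consecutive days of dronedarone non-adherence as discontinued treatment, which points to 7.1, while 7.2 allows non-compliance to end follow-up altogether.

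The decision lies with staff who know the assignment. Only the dronedarone arm has drug shipments, the 10-day start check and drug compliance to assess (Section 6.2), so such withdrawals are plausibly more frequent there. Several safety events of interest in Table 3 (pacemaker implantation, ventricular arrhythmia, heart failure, major bleeding) also appear in Table 1 among the causes of a primary-endpoint hospitalization. A patient withdrawn for safety may therefore be one who is heading for a primary event. If so, censoring is informative, and the hazard ratio no longer estimates the treatment-policy effect that the intent-to-treat definition aims at.

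**Working it through.** **1. The design figure reproduces and is not in question.** Inputs from Section 9.5: hazard ratio 0.79, 733 events, two-sided alpha 0.05. Schoenfeld power = Φ(√733/2 × (−ln 0.79) − 1.96) = Φ(3.191 − 1.96) = Φ(1.231) = 0.891, against 89% stated. The point concerns bias, not power.

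**2. What is recorded after a 7.2 withdrawal.**

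| Outcome component | After stopping drug (7.1) | After investigator withdrawal (7.2) |
|---|---|---|
| Death | Followed to 12 months | Vital status attempted (7.3) |
| Cardiovascular hospitalization | Followed to 12 months | No text continues collection |
| Primary analysis | Counted | Censored, assumed non-informative (9.3.2) |

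**3. Size of the possible bias.** From the protocol: usual-care 12-month incidence 30%, hence a monthly hazard λ = −ln(0.70)/12 = 0.02972. Assumed, because the protocol gives no values: a fraction w of the dronedarone arm is withdrawn evenly over months 0-6; their hazard is θ times that of the rest of the arm; none are withdrawn in usual care; the drug has no true effect.

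Fix the arm-average hazard at λ, so the remaining patients have hazard b = λ/(1 − w + wθ). Compute events per person-month with full follow-up and with the withdrawn group censored. The ratio of the two multiplies the hazard ratio.

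Example, w = 5% and θ = 2: b = 0.02972/1.05 = 0.02831.

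- Remaining 95%: 0.2880 events and 10.174 months per patient.
- Withdrawn 5%, if followed to 12 months: 0.4931 events and 8.709 months per patient.
- Withdrawn 5%, if censored: 0.1521 events and 2.687 months per patient.
- Full follow-up rate: (0.95 × 0.2880 + 0.05 × 0.4931)/(0.95 × 10.174 + 0.05 × 8.709) = 0.2983/10.101 = 0.02953.
- Rate with censoring: (0.95 × 0.2880 + 0.05 × 0.1521)/(0.95 × 10.174 + 0.05 × 2.687) = 0.2812/9.800 = 0.02870.
- Ratio: 0.972.

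One-sided type I error = 1 − Φ(1.96 − z), with z = −ln(ratio) × √800/2. About 800 events are expected under no effect: 2 × 406 = 812 at a constant hazard with 20% loss. Here z = 0.404 and the error is 1 − Φ(1.556) = 0.060.

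A simulation with 400,000 patients per arm, a Cox model, the 10/20/25/30% accumulation of Section 9.5 and 20% background loss gives similar results (noise of a few thousandths in the hazard ratio):

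| w | θ | Multiplier (formula) | Error (formula) | Hazard ratio (simulation) | Error (simulation) |
|---|---|---|---|---|---|
| 1% | 1.5 | 0.997 | 0.028 | 1.00 | 0.027 |
| 1% | 2 | 0.994 | 0.030 | 0.99 | 0.031 |
| 2% | 1.5 | 0.994 | 0.031 | 1.00 | 0.029 |
| 2% | 2 | 0.988 | 0.036 | 0.99 | 0.033 |
| 5% | 1.5 | 0.984 | 0.041 | 0.99 | 0.039 |
| 5% | 2 | 0.972 | 0.060 | 0.97 | 0.055 |

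With a true hazard ratio of 0.79 and θ = 2, the simulated hazard ratio falls to about 0.78 at 2% and 0.77 at 5%.

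**4. Sensitivity to the assumptions, by the formula.**

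- θ = 1: no bias at any w.
- Equal withdrawal in both arms at the same relative risk, no drug effect: no bias.
- 5% in dronedarone against 3% in usual care, θ = 2: ratio 0.989, error about 0.036.
- θ = 0.75, w = 5%: ratio 1.009, against dronedarone.

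**The case against.** A reader might infer that 7.1 and 7.2 contradict each other. They do not: one covers stopping drug, the other leaving the study, and a protocol can hold both. What is missing is a rule for safety or compliance reasons, which fit either. Nor does 7.2 undo the intent-to-treat set, which fixes who is analyzed and in which arm.

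A reader might also infer that the bias is certain, arises in one arm only and favors dronedarone. The text does not support this. Section 7.2 covers both arms, behavioral reasons are neutral as to arm, and compliance can mean more than drug intake: Section 5.1 asks every participant to comply with the protocol, and Section 6 requires anticoagulation (by score) and rate control in all. Zero withdrawals in usual care is a worst case. Withdrawals prompted by rash or diarrhea need not mark higher cardiovascular risk. Figures at 10% withdrawal (multiplier 0.946-0.970, error 0.064-0.12 for θ of 1.5-2) sit poorly with a rule expected to be used uncommonly.

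The safeguards count too. Vital status protects the death component, a final form is completed at early withdrawal, and censoring is at the last date of known status, which need not be the withdrawal date. A sensitivity analysis for informative censoring may be in the SAP, which is not shown.

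All of this limits size and certainty. It does not remove the point: no text continues collection of hospitalizations after an investigator withdrawal, and no later analysis can restore events that were not collected.

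**Conclusion.** The point holds as an overlap without a dividing rule that may cause differential, informative censoring of cardiovascular hospitalizations. The direction is conditional: it favors dronedarone only if withdrawals are more frequent in that arm and those withdrawn are at higher risk. Both are plausible; neither is stated.

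At the frequency nearest to the protocol's own expectation, taken here as 1-2% of the dronedarone arm, the effect is small: a multiplier of about 0.99 and one-sided error of about 0.028-0.036. At 5% it is worth avoiding: about 0.97-0.98 and 0.04-0.06. These figures rest on assumed frequency, relative hazard and timing, and on no withdrawals in usual care. The change is worth making because the loss is avoidable at little cost, not because a large bias has been shown.

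**What to change.** Reconcile 7.2 with 7.1:

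- Investigator-initiated withdrawal for safety, behavioral or compliance reasons ends study intervention only.
- Outcome follow-up then continues to 12 months through the existing 6- and 12-month encounters, which Section 8 already allows to be virtual, or by record review.
- Only the participant's own withdrawal of consent ends data collection.
- The initiator and the reason for each withdrawal are recorded and tabulated by arm.

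Section 7.3 needs no change on this account: it already requires repeated contact attempts and a vital status search, and defines loss by failure to complete the 12-month visit. The decision to stop drug is not affected.

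The cost is a short amendment, a note to sites and some additional follow-up contacts.
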